13.1 CRITERIA FOR REMOVAL FROM STUDY

Patients should **permanently** discontinue treatment with avelumab for the reasons enumerated in Section 9 or in the event of:

- Intolerable adverse events (e.g. CTCAE v4.0 grade 3 or 4) that cannot be managed by dose modification or delay
- Further dose modification or delay considered necessary but not allowed per protocol section 9.4
- Pregnancy¹
- Withdrawal of informed consent²
- If the treating physician determines that it is in the best interest of the patient to stop study drug
- Non-compliance with the defined treatment plan

Patients will be removed from study after treatment ends in the event of:

- Death
- Pregnancy¹
- Withdrawal of informed consent²
- Non-compliance with the defined follow up studies

¹Pregnancy: In case of a patient or the patient's partner becoming pregnant during the trial the investigational drug has to be immediately stopped and the patients must be followed-up until birth or other termination of the pregnancy. Repeat counseling on birth defect risk must be offered.

²Consent withdrawal: in case a patient withdraws his/her consent for taking drug, it is of utmost importance for the robustness and integrity of the trial results that his/her safety data are recorded until the end of the 52 weeks period. Thus, all patients will be asked to follow their visit schedule until 52 weeks.

Patients who discontinue from this trial are not allowed to be reenrolled in this trial. Patients who discontinue medication within the first two weeks (during the washout period) will be replaced. For the patients who stopped trial before enrollment, their data will be part of the description of the screening population.

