4.4 Estimated Duration of Subject Participation

Subjects may be treated with avelumab for up to 24 months. All subjects will be followed for survival and assessed every 2 months as per Section 10 for up to 1 year following completion of avelumab or disease progression unless the Principal Investigator or Pfizer elects to end the study.

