10.8 Followup Period Visits (every 2 months +/- 14 days)

Patients will be seen and evaluated by a physician every 2 months during the follow-up period. They will undergo standard of care serial imaging as per Section 10.5, blood work (CBC, CMP, Free T4/TSH), and a history and physical examination.

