12.0 CRITERIA FOR THERAPEUTIC RESPONSE/OUTCOME ASSESSMENT

For the purposes of this study, patients will be evaluated for response every 2 months after completing SBRT (approximately 8 weeks, or every 4 cycles). Modified RECIST for mesothelioma and RECIST 1.1 criteria will be used [22]. CT scan of the chest, abdomen, and pelvis will be used for response assessment. The companion CT from an integrated PET/CT examination is suitable for this requirement. As part of the secondary endpoints, progression-free and overall survival will be recorded. Progression-free survival is defined as the length of time from the start of active treatment (avelumab) until removal from study due to progressive disease (defined by modified RECIST 1.1) or death. Removal from study due to toxicity will be counted as censoring. Overall survival is defined as the length of time from the start of active treatment until d e a t h .

Modified RECIST for Mesothelioma [23, 24]

The modified RECIST criteria for mesothelioma use unidimensional measurements of tumor thickness perpendicular to the chest wall or mediastinum. In our protocol, the irradiated lesion is not required to be intrathoracic. This is measured on CT scan in 2 sites at 3 different levels at least 1cm apart. At reassessment, the thickness must be measured at the same position and level. Exhaustive documentation of non-measurable lesions are not required. The sum of tumor diameters is used to measure response.

Definitions of Overall Response	
Complete Response (CR)	Disappearance of all target lesions who no evidence of tumor elsewhere.

Partial Response (PR)	At least a 30% decrease in the sum of diameters of target lesions, taking as reference the baseline sum diameters.
Stable Disease (SD)	Response neither meeting the criteria of CR, PR or PD
Progressive Disease (PD)	At least a 20% increase in the sum of diameters of tumor measurements over the nadir measurement, or appearance of one or more new lesions.

RECIST 1.1

Evaluation of target lesions	
Complete Response (CR)	Disappearance of all target lesions Any pathological lymph nodes (whether target or non-target) must have reduction in short axis to <10 mm.
Partial Response (PR)	At least a 30% decrease in the sum of diameters of target lesions, taking as reference the baseline sum diameters.
Stable Disease (SD)	Neither sufficient shrinkage to qualify for PR nor sufficient increase to qualify for PD, taking as reference the smallest sum of diameters while on study.

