14.0 BIOSTATISTICS

The primary endpoint, the safety of a combination of avelumab and SBRT, will be defined based on the rate of any grade 3 or higher non-hematologic toxicity within the first 3 months after SBRT (for the rest of the section this will be referred to as AE). A two-stage stopping rule will be used to protect patients' safety. If 3 or more among the first 13 patients develop AEs, then the trial will be stopped and declared unsafe. Otherwise, an additional 14 patients will be enrolled and treated. If, among the total 27 patients, 5 or more patients are observed to have AEs, then the trial will also be declared unsafe. This stopping rule has a power of 80% declaring the true AE rate of 0.1 or lower safe, and a type 1 error rate (alpha) of 5% declaring true AE rate of 0.3 or higher safe.

For secondary endpoints, the overall response and the irradiated lesion and non-irradiated lesion response rates (4 months from start date of the combined therapy) based on RECIST 1.1 response criteria will be summarized by sample proportions and their confidence intervals. PFS and OS will be evaluated by Kaplan-Meier method.

For the exploratory objectives, we will evaluate changes of T-cell infiltration and serum immunophenotype at baseline and after SBRT + immunotherapy both in- and outside the irradiated field. The former is measured as numerical values so we will use Wilcoxon signed-rank test. The latter is categorical so we will tabulate it and employ the marginal homogeneity test. Due to the expected small sample size, results will be interpreted cautiously. The imaging studies using DWI-MRI and DCE-MRI, and FDG-PET will be correlated with biopsy results by McNemar's tests.

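### Sections 4.4 and 13.1 conflict on survival follow-up of patients who miss follow-up studies, and the plan gives no censoring rule for overall survival

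*Combined protocol and SAP*

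**What the plan says.** Section 4.4 commits to survival follow-up without regard to compliance: "All subjects will be followed for survival and assessed every 2 months as per Section 10 for up to 1 year" after completion of avelumab or progression. The single exception is that the Principal Investigator or the drug supplier "elects to end the study".

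Section 13.1 has two lists. The first gives reasons to stop avelumab. The second opens "Patients will be removed from study after treatment ends in the event of", and its entries are death, pregnancy, withdrawal of consent and "Non-compliance with the defined follow up studies". A footnote to withdrawal of consent asks patients who stop taking drug to keep to their visits until 52 weeks so that safety data are complete. The non-compliance entry has no such footnote.

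Section 10.8 defines what follow-up consists of: "Patients will be seen and evaluated by a physician every 2 months during the follow-up period", with imaging, blood work, history and examination.

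Section 12.0 gives the endpoint: "Overall survival is defined as the length of time from the start of active treatment until" death. The only censoring statement there concerns removal for toxicity and is attached to progression-free survival (PFS). Section 14.0 adds only that "PFS and OS will be evaluated by Kaplan-Meier method".

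**The concern.** The two sections give site staff opposite instructions for the same patient. Someone who stops attending after treatment is to be followed for survival under Section 4.4 and removed from the study under Section 13.1. Section 4.4 also refers survival follow-up to Section 10, where follow-up means seeing a physician, and the study calendar has no entry for vital status alone. A patient removed for missing those visits therefore has no planned route by which a later death would be recorded.

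Kaplan-Meier estimation assumes that a censored patient has the same outlook as those still followed. Section 3.1 describes a disease that is nearly always fatal, with mean survival of 8 to 13 months. It is plausible that some patients miss a two-monthly visit and CT because they are too ill to travel. If they are censored at that point, their deaths drop out of the estimate. OS is a named secondary endpoint, and vital status not collected at the time may be hard to recover later.

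**Working it through.** The plan states no target, event count or dropout rate for OS, so there is no figure of its own to reproduce. The check is a comparison of the texts followed by an illustration under assumptions.

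**Texts side by side**

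| Question | Section 4.4 | Section 13.1 |
|---|---|---|
| Who is covered? | All subjects | Patients whose treatment has ended |
| Does non-compliance end follow-up? | Not listed as an exception | Yes, removal from study |
| Is vital status collected afterwards? | Implied for up to 1 year | Not mentioned |
| How is OS censored? | Not stated | Not stated; Sections 12.0 and 14.0 are also silent |

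**Illustration: inputs**

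- True median OS 7.5 months, the midpoint of the two arm medians (7.7 and 7.3) of the tremelimumab trial described in Section 3.2. Exponential survival is assumed.
- Removal no earlier than month 4, because Section 13.1 acts only after treatment ends. Month 4 is an assumption.
- Removal 2 months before death (assumed).
- Share of all patients removed, f = 5%, 10% or 20% (assumed).

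**Illustration: formulas**

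The hazard is λ = ln 2 / 7.5 = 0.0924 per month, and S(t) = exp(−λt). True 12-month OS is S(12) = 0.330. Only patients who die after month 6 can be removed, and S(6) = 0.574. The fraction removed among them is g = f / 0.574, which is 0.087, 0.174 or 0.348.

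The hazard that Kaplan-Meier estimates when removal is treated as censoring is:

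- before month 4: λ
- months 4 to 6: λS(t) / [S(t) − g(S(6) − S(t+2))]
- after month 6: λ(1 − g) / [(1 − g) + g·exp(−2λ)], with exp(−2λ) = 0.831

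Worked for f = 10%: after month 6 the hazard is 0.0924 × 0.826 / (0.826 + 0.174 × 0.831) = 0.0786. The curve at month 6 is 0.573. Then 12-month OS = 0.573 × exp(−6 × 0.0786) = 0.357, and the median = 6 + ln(0.573/0.5)/0.0786 = 7.7 months.

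| Removed (of 27) | Hazard after month 6 | Median, months | 12-month OS |
|---|---|---|---|
| none | 0.0924 | 7.5 | 33% |
| 5% (1.35) | 0.0856 | 7.6 | 34% |
| 10% (2.7) | 0.0786 | 7.7 | 36% |
| 20% (5.4) | 0.0640 | 8.1 | 39% |

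A simulation of 1,000,000 patients agrees with these values to within rounding.

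**Direction**

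A second simulation leaves the direction open. It uses mean survival of 8, 10.5 or 13 months (Section 3.1), a removal hazard of 0.02 or 0.05 per month from month 4, and a 24-month cut-off. It compares 12-month OS censored at removal with 12-month OS when all deaths are counted:

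| Death hazard after removal | Shift in 12-month OS, points |
|---|---|
| Halved | −1.0 to −2.4 |
| Unchanged | 0.0 |
| Doubled | +1.2 to +3.5 |
| Tripled | +1.9 to +5.9 |

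**Sampling error**

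With 27 patients and no censoring, the standard error of 12-month OS is √(0.33 × 0.67 / 27) = 0.09, or 9 points. The simulated standard deviation of the median is 2.1 months, with a 95% range of about 4 to 12 months. At f = 10% the shifts are 0.2 month and about 3 points.

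**The case against.** The strongest reply is that the sections can be read together: Section 13.1 ends study visits, while Section 4.4 separately governs survival status for everyone. On that reading deaths after removal are still counted and nothing is lost. This is possible, but the text does not say it. Section 13.1 puts non-compliance in the same list as death and withdrawal of consent, and no section describes how vital status would be obtained without visits.

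A reader might infer that the plan censors sick patients and so inflates OS. The documents do not support that. No passage says that OS is censored at removal, and the one censoring statement belongs to PFS. Nor does any passage say who becomes non-compliant. Upward bias needs both steps, and the second simulation shows that even its sign depends on the second.

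A reader might also apply removal from the first day, which gives medians of about 7.9, 8.2 and 9.1 months for 5, 10 and 20% removed. That does not fit a rule that acts only after treatment ends. It is also tempting to say that a few removals would show in a trial of 27. They would not stand out from sampling error of the size shown above.

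It is fair, too, that no decision rests on OS. It is descriptive, in a single arm, with no target or comparator.

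**Conclusion.** The conflict between Sections 4.4 and 13.1 is real, and so is the absence of an OS censoring rule. Following Section 13.1 as written would probably lose survival data on patients who may be at higher risk.

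The resulting bias is a conditional risk. It is upward if removed patients are sicker, absent if their risk is unchanged, and downward if it is lower. With 10% (5 to 20%) of all patients removed 2 months before death from month 4 onward, the median reads 7.7 (7.6 to 8.1) months against 7.5, and 12-month OS reads 36% (34 to 39%) against 33%. The removal share, the 2-month lead, the month-4 start and the exponential form are all assumptions, since the documents give none of them.

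The sample size and the two-stage toxicity rule do not use OS and are unaffected. This is a cheap improvement of low severity.

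**What to change.** Reconcile the two sections with a short addition to Section 13.1: non-compliance with visits or imaging ends scheduled study assessments only; vital status continues to be collected by phone, chart or public record for the period in Section 4.4, unless the patient withdraws consent for that. Add to Section 12.0 or 14.0 that OS is censored at the date last known alive.

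The cost is a few lines of text and occasional phone or chart checks by the coordinator already assigned under Section 16.1. Phone contact is already accepted for the 90-day safety visit, so no new procedure is needed.

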14.0 BIOSTATISTICS

The primary endpoint, the safety of a combination of avelumab and SBRT, will be defined based on the rate of any grade 3 or higher non-hematologic toxicity within the first 3 months after SBRT (for the rest of the section this will be referred to as AE). A two-stage stopping rule will be used to protect patients' safety. If 3 or more among the first 13 patients develop AEs, then the trial will be stopped and declared unsafe. Otherwise, an additional 14 patients will be enrolled and treated. If, among the total 27 patients, 5 or more patients are observed to have AEs, then the trial will also be declared unsafe. This stopping rule has a power of 80% declaring the true AE rate of 0.1 or lower safe, and a type 1 error rate (alpha) of 5% declaring true AE rate of 0.3 or higher safe.

For secondary endpoints, the overall response and the irradiated lesion and non-irradiated lesion response rates (4 months from start date of the combined therapy) based on RECIST 1.1 response criteria will be summarized by sample proportions and their confidence intervals. PFS and OS will be evaluated by Kaplan-Meier method.

For the exploratory objectives, we will evaluate changes of T-cell infiltration and serum immunophenotype at baseline and after SBRT + immunotherapy both in- and outside the irradiated field. The former is measured as numerical values so we will use Wilcoxon signed-rank test. The latter is categorical so we will tabulate it and employ the marginal homogeneity test. Due to the expected small sample size, results will be interpreted cautiously. The imaging studies using DWI-MRI and DCE-MRI, and FDG-PET will be correlated with biopsy results by McNemar's tests.

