Anti-PD-1/PD-L1 agents have shown some significant promise. At the 2015 AACR, Alley et al. presented the mesothelioma results of the KEYNOTE-028 trial, a non-randomized multi-cohort phase IB study of pembrolizumab for PD-L1 positive solid advanced tumors. In this cohort of 38 patients (out of 84 screened), each had $\geq 1\%$ PD-L1 expression in tumor cells or PD-L1-positive stromal bands. The primary endpoint was safety, tolerability, and preliminary efficacy. 88% had received at least one line of prior therapy, most of which was a platinum-based agent in combination with pemetrexed. Treatment was pembrolizumab 10mg/kg every 2 weeks for up to 2 years, or until confirmed progression of disease. 60% of patients experienced a drug-related adverse event, although only 12% (3 patients) experienced grade 3 or higher toxicity. No patients discontinued therapy due to drug-related events. There was a 76% disease control rate, which was remarkable (24% overall response rate, with 52% stable disease). Given this significant response rate and potential for additional improvement, the role of immunotherapy, particularly with PD-L1 inhibitors is certainly warranted.

Data on safety and early efficacy information on avelumab in mesothelioma were first presented at the ASCO 2016 Annual Meeting by Hassan et al. 53 patients with unresectable pleural or peritoneal mesothelioma were recruited. These patients had progressed after a platinum-pemetrexed-containing regimen and were unselected for PD-L1 expression. They were treated with avelumab 10 mg/kg IV every 2 weeks until progression, unacceptable toxicity, or withdrawal. Tumors were assessed every 6 weeks (RECIST 1.1). Patients were followed for a median of 46 weeks. The overall response rate was 9.4% (5 partial responses; 95% CI: 3.1, 20.7) and an additional 4 were ongoing. Stable disease was observed in 25 patients (47.2%). This yielded a disease control rate of 56.6%. Median progression-free survival was 17.1 weeks (95% CI: 6.1, 30.1), and PFS rate at 24 weeks was 38.4% (95% CI: 23.3, 53.4). Grade ≥ 3 treatment-related adverse events occurred in 4 patients (7.5%). This included colitis, decreased lymphocytes, and increased GGT or CPK. There were no treatment-related deaths. These data indicate that avelumab has a reasonable toxicity profile and favorable activity in a PD-L1 unselected population. We note that this study was in an unselected cohort of patients.

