- Severe (CTCAE Grade 3): Incapacitating signs/symptoms which cause considerable interference with the subject's daily activities, unacceptable
- Life-threatening (CTCAE Grade 4): Life-threatening or disabling AE
- Death (CTCAE Grade 5): Death-related AE.

Definition of Serious Adverse Event

The following definition of SAE applies for the study: "a serious AE means any AE occurring at any dose that results in any of the following outcomes: death, a life-threatening AE, inpatient hospitalization or prolongation of existing hospitalization, a persistent or significant disability/incapacity, a congenital anomaly/birth defect, or overdose of study drug. Important medical events that may not result in death, be life threatening, or require hospitalization may be considered a serious AE when, based upon appropriate medical judgment, they may jeopardize the subject, or the subject may require medical or surgical intervention to prevent one of the outcomes listed in this definition. A life-threatening AE is any AE that places the subject, in the view of the investigator, at immediate risk of death from the reaction as it occurred (e.g., it does not include a reaction

that, had it occurred in a more severe form, might have caused death)." Refer to section 17.2 for "Reporting and Treating Serious Adverse Events."

Pregnancies

Although pregnancy and lactation are not considered adverse events, it is the responsibility of investigators or their designees to report any pregnancy or lactation in a subject (spontaneously reported to them), including the pregnancy of a male subject's female partner that occurs during the trial or within 120 days of completing the trial, or 30 days following cessation of treatment if the subject initiates new anticancer therapy, whichever is earlier. All subjects and female partners of male subjects who become pregnant must be followed to the completion/termination of the pregnancy. Pregnancy outcomes of spontaneous abortion, missed abortion, benign hydatidiform mole, blighted ovum, fetal death, intrauterine death, miscarriage and stillbirth must be reported as serious events (Important Medical Events). If the pregnancy continues to term, the outcome (health of infant) must also be reported. Such events must be reported within 5 calendar days to the MSKCC Safety Office and within 2 working days to Pfizer Safety (Pfizer U.S. Clinical Trial Department, [contact], OR [contact] specifying Protocol, Subject, Site/PI, and SAE/Onset).

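### The two-stage safety rule counts a treatment-related death the same as a grade 3 event, and the protocol states no study-level trigger for a toxic death

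*Combined protocol and SAP*

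**What the plan says.** Section 14.0 defines the primary endpoint as "the rate of any grade 3 or higher non-hematologic toxicity within the first 3 months after SBRT". The severity scale in Section 11.1.1 runs up to "Death (CTCAE Grade 5): Death-related AE", so a non-hematologic toxic death inside the window is one event of this kind.

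Two boundaries follow. At stage 1: "If 3 or more among the first 13 patients develop AEs, then the trial will be stopped and declared unsafe". With two or fewer events the instruction is "Otherwise, an additional 14 patients will be enrolled and treated". At the end: "If, among the total 27 patients, 5 or more patients are observed to have AEs, then the trial will also be declared unsafe". For the acceptable rate the plan claims: "This stopping rule has a power of 80% declaring the true AE rate of 0.1 or lower safe". At a true event rate of 30% or more, it puts the chance of a safe verdict at 5% and treats this as its type 1 error.

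Other sections bear on oversight:

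- Section 16.3 places the trial under DSMC review from the first enrolment and refers to an institutional monitoring plan.
- Section 17.3 sets timelines and content for serious adverse event reports. Section 17.3.1 requires immediate reporting of deaths to the supplier.
- Section 4.4 recognises that the investigator or the supplier may end the study.

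None of these names a death as a reason to pause accrual or to withhold a favourable verdict.

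**The concern.** Safety is the primary endpoint, and Section 14.0 gives patient protection as the purpose of the rule. The boundaries are set for a mixed grade 3+ rate of 10% against 30%. A 10% rate of mostly grade 3 events may be acceptable where a 10% rate of toxic deaths would not be, yet the rule treats the two alike.

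The protocol calls the combination novel and says in Section 3.3 that no clinical results exist yet for radiotherapy with anti-PD-L1 treatment. For the 53-patient avelumab study, Section 3.2 reports: "There were no treatment-related deaths". Against that background one or two toxic deaths would be an important signal. The prespecified rule would not act on them unless enough other events occurred as well.

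**Working it through.** **Inputs from Section 14.0.** Stage 1: n = 13, continue if X1 ≤ 2. Stage 2: n = 14 more, not unsafe if X1 + X2 ≤ 4. The section does not spell out the safe outcome, but its power statement implies that it is the complement of unsafe.

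**1. Reproduce the plan's figures.** With b(x; n, p) the binomial probability,

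P(safe) = Σ over x = 0, 1, 2 of b(x; 13, p) × P(Bin(14, p) ≤ 4 − x).

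- p = 0.10: 0.2542 × 0.9908 + 0.3672 × 0.9559 + 0.2448 × 0.8416 = 0.2518 + 0.3510 + 0.2060 = 0.809 (stated 80%).
- p = 0.30: 0.0097 × 0.5842 + 0.0540 × 0.3552 + 0.1388 × 0.1608 = 0.0057 + 0.0192 + 0.0223 = 0.047 (stated 5%).

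Both agree with the plan.

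**2. Apply the rule to deaths alone.**

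- Two toxic deaths in the first 13 (2/13 = 15.4%) and no other event: the count is 2, below 3, so 14 more patients are enrolled.
- Four toxic deaths in 27 (4/27 = 14.8%), at most two of them in the first 13, and no other event: the count is 4, below 5, so the unsafe boundary is not met.
- If three or four of the four fall in the first 13, the rule stops the trial. With random placement this has probability (C(13,3) × 14 + C(13,4)) / C(27,4) = (4004 + 715) / 17550 = 27%.

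**3. Probability of a safe verdict with two or more toxic deaths.** The documents give no fatal-toxicity rate for the combination. Assume a fatal rate d = 5% and a non-fatal grade 3+ rate f, with p = d + f. Each event is then fatal with probability q = d/p. For each total T of 2, 3 or 4 inside the safe region, multiply its probability by P(Bin(T, q) ≥ 2) and add.

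- f = 0: q = 1, so 0.2434 + 0.0963 + 0.0247 = 0.364.
- f = 7.5%: p = 0.125, q = 0.4, so 0.1947 × 0.160 + 0.2091 × 0.352 + 0.1452 × 0.525 = 0.181.
- f = 10%: p = 0.15, q = 1/3, so 0.1358 × 0.111 + 0.1802 × 0.259 + 0.1546 × 0.407 = 0.125.

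| Assumed non-fatal rate f (fatal 5%) | P(safe) | P(safe and ≥2 toxic deaths) |
|---|---|---|
| 0 | 0.970 | 0.364 |
| 7.5% | 0.681 | 0.181 |
| 10% | 0.542 | 0.125 |
| 15% | 0.293 | 0.051 |

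The 7.5% is borrowed for scale from the grade ≥3 treatment-related rate with avelumab alone (4 of 53, Section 3.2). That count includes decreased lymphocytes, so it is not exactly the rate of this endpoint.

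**4. Sensitivity to the fatal rate.** P(≥2 toxic deaths among 13) is 0.7%, 2.7% and 13.5% at assumed fatal rates of 1%, 2% and 5%. The one-sided 95% upper bound from 0 of 53 is 1 − 0.05^(1/53) = 5.5%, so 5% lies near the top of what the avelumab-alone data allow.

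**5. What the count leaves out.** Read literally, a toxic death before SBRT, more than 3 months after it, or from hematologic toxicity is not counted at all. Avelumab starts two cycles before SBRT and may continue for 24 months (Sections 4.3 and 9.1.1).

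**The case against.** A pooled grade 3+ endpoint is an ordinary safety definition, and its stated properties are correct. Severity is not ignored: it is the threshold for counting. What is missing is only extra weight above grade 3.

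A reader might infer that four toxic deaths in 27 would always pass. They pass only if no more than two fall in the first 13 and nobody else has an event. At a 5% fatal rate, a safe verdict with exactly four deaths has probability 2.5% with no other events and 0.2% to 0.4% with 10% or 7.5% added non-fatal events.

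A reader might also infer that the rule is nearly powerless against toxic deaths, from the 97% chance of a safe verdict at a 5% fatal rate. That figure sets every other toxicity to zero. With 7.5% non-fatal events it falls to 68%, because non-fatal events move the same count.

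Nor do the documents support the reading that the trial could not be stopped. A stopping rule does not bar an earlier halt. Under Sections 4.4, 16.3, 17.3 and 17.3.1 the DSMC reviews the trial throughout, deaths are reported at once to the supplier, and the investigator or supplier may end it. The institutional monitoring plan and the ethics board's reporting procedure are cited but not reproduced, so a hold after a related death may exist there.

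Finally, the risk should not be framed as thoracic irradiation only: Section 12.0 says the irradiated lesion need not be in the chest.

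All of this limits the size of the concern. What remains is that Section 14.0 directs further enrolment, and can lead to a safe verdict, with no stated step for reviewing a death.

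**Conclusion.** The point holds as a gap in the prespecified rule. Two toxic deaths in 13 with no other event open stage 2. Four in 27, under the two conditions given above, do not meet the unsafe boundary. Oversight that could intervene is discretionary in these documents and has no stated trigger.

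The size depends on assumed rates. At a 5% fatal rate, a safe verdict despite two or more toxic deaths has probability 36%, 18% or 12% with 0, 7.5% or 10% added non-fatal events. It is smaller if the fatal rate is lower. The calculation also assumes independent patients and deaths that fall inside the endpoint window. There is no error in the 80% and 5% figures, and no case for moving the boundaries. This is a cheap improvement and not a flaw that invalidates the design.

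**What to change.** Add to Section 14.0:

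1. Any death judged at least possibly related to avelumab or SBRT, whenever it occurs, suspends new accrual until the DSMC has reviewed it.
2. The DSMC reviews all grade 5 events before the combination is declared safe.
3. Grade 3, 4 and 5 counts are reported separately beside the 13- and 27-patient totals.

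Keep the numerical boundaries. State that the review is not an automatic veto, so that the 80% and 5% figures describe the numerical boundary only. This wording matters: if a single toxic death blocked a safe verdict, P(safe) at a 10% event rate would fall from 0.81 to 0.65, 0.51 or 0.24 at assumed fatal rates of 1%, 2% or 5%.

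The cost is a few sentences and possible short pauses, which are modest at the planned accrual of about one patient per month. The chance of a safe verdict would be somewhat lower when toxic deaths occur. By how much depends on the DSMC's decisions and cannot be calculated in advance. All events are already graded under Section 11.1.1, so the separate counts need no new data.

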Study Design	
This clinical trial will be designed as a single-arm, single-institution safety study at Memorial Sloan Kettering Cancer Center Main Campus and Regional Sites. The main objective is to evaluate the safety of a novel combination of avelumab (anti-PD-L1 mAb) and stereotactic body radiation therapy (SBRT) for advanced malignant pleural and peritoneal mesothelioma (MPM).
 
The treatment will consist of one dose of avelumab every other week as well as a short course of SBRT after the first two doses of avelumab. Avelumab will be continued up to 24 months or until disease progression. To further enhance our current understanding of tumor immunology as well as prognostic biomarkers, we will collect peripheral serum samples before, during and after treatment, and tumor biopsies of the irradiated and an unirradiated lesion (if available) before and after radiation.
 
The safety endpoint of the trial will be assessed based on grade 3 or higher non-hematologic toxicity.
 
We hypothesize that the combination of immunotherapy and SBRT will be safe and well tolerated. Furthermore, we believe that this combination therapy will lead to an increase in tumor-specific T-cells and neoantigen diversity along with a higher T-cell infiltration of irradiated and unirradiated tumor lesions and objective overall responses in lesions both in and outside the radiation field.
 
Accrual is estimated to be 1 patient per month.

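### Section 14 sets no accrual stop at the 5th AE in stage 2 and leaves the timing of the stage 1 stop open, so patients can be enrolled after the unsafe verdict is already fixed

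*Combined protocol and SAP*

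**What the plan says.** Section 14 gives the rule a protective purpose: "A two-stage stopping rule will be used to protect patients' safety". The event counted, which that section calls an AE, is the "rate of any grade 3 or higher non-hematologic toxicity within the first 3 months after SBRT".

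The two boundaries are worded differently.

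- Stage 1: "If 3 or more among the first 13 patients develop AEs, then the trial will be stopped and declared unsafe".
- Stage 2: "Otherwise, an additional 14 patients will be enrolled and treated", and then "If, among the total 27 patients, 5 or more patients are observed to have AEs, then the trial will also be declared unsafe".

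The first boundary orders a stop. The second orders only a declaration, counted over all 27. Two properties are claimed. One is an 80% chance of calling the regimen safe when its true AE rate is at most 0.1. The other is the "type 1 error rate (alpha) of 5% declaring true AE rate of 0.3 or higher safe".

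The shorter accounts of the design in Sections 1.0 and 4.2 repeat the 13 + 14 structure and add no stop within a stage. Section 16.3 describes general review by the institutional monitoring committee and does not link it to the counts of 3 or 5.

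**The concern.** Once 5 patients have had an AE, no later outcome can bring the total back to 4 or fewer. The same holds for the 3rd AE in stage 1. From that moment a new patient adds nothing to the primary conclusion and is exposed to a regimen that the rule must call unsafe. A rule written to protect patients would be expected to halt accrual there. In stage 2 the text does not. In stage 1 it orders a halt but does not say whether this acts at the 3rd AE or only when all 13 have been assessed.

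At stake is the number of patients enrolled after the deciding event. The error rates are not affected.

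**Working it through.** **Inputs.** From Section 14: 13 then 14 patients; stop at 3 or more AEs of 13; unsafe at 5 or more of 27; true rates 0.10 and 0.30; AE window of 3 months after SBRT. From Section 1.0: "Accrual is estimated to be 1 patient per month". From Section 9.1.1 and the Section 10 calendar: SBRT follows two 2-week cycles, at about day 29. The rate 0.20 is added here as a midpoint. AEs are taken as independent between patients.

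**Step 1: reproduce the plan's figures.** With b(n,x,p) the binomial probability,

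P(safe) = Σ over x = 0, 1, 2 of b(13,x,p) × P(Bin(14,p) ≤ 4 − x).

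- p = 0.10: 0.2542×0.9908 + 0.3672×0.9559 + 0.2448×0.8416 = 0.809, against the stated 80%.
- p = 0.30: 0.0097×0.5842 + 0.0540×0.3552 + 0.1388×0.1608 = 0.047, against the stated 5%.

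Both agree, with 5% read as a ceiling because the design is discrete.

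**Step 2: effect of a stop on these figures.** A stop at the 3rd AE (stage 1) or the 5th (stage 2) acts only on trials already bound to be declared unsafe. An exact patient-by-patient recursion with both stops gives the same 0.809 and 0.047.

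**Step 3: how often the 5th AE is reached in stage 2.** This is P(enter stage 2) − P(safe):

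- 0.10: 0.8661 − 0.8088 = 0.0573
- 0.20: 0.5017 − 0.2927 = 0.2090
- 0.30: 0.2025 − 0.0472 = 0.1553

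**Step 4: the lag.** Read literally, no countable AE occurs before SBRT, about one month after first dose, and the window closes about four months after first dose. At one patient per month, an AE becomes known 1 to 4 enrolments after the patient who has it.

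**Step 5: patients spared by the stage 2 stop alone.** The 5th AE falls on stage 2 patient j with probability

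Σ over x = 0, 1, 2 of b(13,x,p) × C(j−1, 4−x) p^(5−x) (1−p)^(j−5+x).

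With a lag of L patients, max(0, 14 − j − L) are spared.

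| True rate | 5th AE reached | Spared in those trials: L = 0 / 1 / 4 | Averaged over all trials: L = 0 / 1 / 4 |
|---|---|---|---|
| 0.10 | 5.7% | 3.1 / 2.3 / 0.7 | 0.18 / 0.13 / 0.04 |
| 0.20 | 20.9% | 4.0 / 3.1 / 1.2 | 0.84 / 0.66 / 0.25 |
| 0.30 | 15.5% | 5.2 / 4.2 / 1.9 | 0.80 / 0.66 / 0.30 |

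The last column is the product of the two before it, for example 0.1553 × 4.246 = 0.66. A simulation with AE times spread evenly over months 1 to 4, and an assumed 4-month hold between stages, gives 1.7, 2.4 and 3.4 spared in the trials that cross. These lie inside the L = 1 to 4 range.

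**Step 6: stage 1, only if read as waiting for all 13.** Expected enrolment at 0.30 without early stops is 13 + 14 × 0.2025 = 15.83. The 3rd AE falls on patient i with probability C(i−1,2) p³ (1−p)^(i−3), and max(0, 13 − i − L) are spared. Averaged over all trials this is 3.17 for L = 1 and 1.33 for L = 4. With both stops:

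- L = 1: 15.83 − 0.66 − 3.17 = 12.0
- L = 4: 15.83 − 0.30 − 1.33 = 14.2

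If the stage 1 sentence already acts at the 3rd AE, the 3.17 or 1.33 belongs to the plan as written, and only the stage 2 term is gained.

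**The case against.** The strongest reply is that stage 1 is already covered. Section 14 orders a stop, its condition is met when the 3rd AE occurs, and the section calls the whole thing a stopping rule. This largely stands: in stage 1 only the timing is unstated. It matters for size. A reader might take the gain at a true rate of 0.30 to be a fall in expected enrolment from 15.8 to 11.1. That needs immediate knowledge of every AE and a stage 1 that runs to 13 regardless, and 3.9 of the 4.7 patients saved come from stage 1. The schedule does not support zero lag for an endpoint that starts at SBRT.

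Second, nothing obliges accrual to go on. Section 1.0 gives 27 as a maximum, Section 4.4 lets the investigator or drug supplier end the study, and committee review begins with the first enrolment (Section 16.3). So a reader who infers that patients will be exposed after the verdict goes too far; they can be. These provisions soften the gap but do not close it, since none is tied to the 5th AE.

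Third, stopping early has a price for the response, survival and biopsy objectives, and stopping on an event biases the simple AE proportion upward. That is true, but it applies only to trials that have already failed on safety.

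In the other direction, the 4-patient lag is near a worst case: AEs are assessed at each visit (Section 11.2) and recorded every cycle, so most would be known before the window closes.

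**Conclusion.** The gap is real and small. Section 14 ties no stop to the 5th AE in stage 2 and does not time the stage 1 stop, so patients can be enrolled when the verdict can no longer change. For stage 2 alone the average cost is below one patient per trial at each rate examined. In the trials that do cross, it is roughly 1 to 4 patients. The larger fall in expected enrolment at 0.30, from 15.8 to between 12.0 and 14.2, applies only if stage 1 waits for all 13.

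The figures rest on independent AEs, one enrolment per month, SBRT about a month after first dose, and a stage 1 verdict known before stage 2 opens. Faster accrual, or the SBRT delay of up to 6 weeks allowed in Section 9.1.2, would lengthen the lag and shrink the saving.

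A reader might also infer that the sample size, power or alpha is wrong. They are not: the stated 80% and 5% reproduce. This is a cheap improvement to how the rule is applied.

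**What to change.** Add one sentence to Section 14: *accrual stops as soon as the 3rd patient with an AE is observed in stage 1, or the 5th cumulative patient with an AE is observed in stage 2, and the regimen is then declared unsafe.* Add that the probabilities of declaring the regimen safe (80.9% at a true rate of 0.10, 4.7% at 0.30) are unchanged. Limit that statement to these probabilities, because expected enrolment and the AE-rate estimate do change.

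The sentence concerns accrual only. The management of patients already on treatment is a clinical matter outside this point.

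The cost is one sentence and, in trials that have already failed on safety, fewer patients for the response, survival and biopsy estimates. In those trials the report should note that the simple AE proportion is biased slightly upward by stopping on an event.
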